2.0 Objectives*

2.1 Aim 1: To enlist community partners as citizen scientists to: identify and recruit Georgia residents with a personal/family history of ovarian cancer, generate content, and collaborate on a scalable message-based outreach intervention to reach ovarian cancer survivors and close relatives (i.e., first- and second-degree relatives) to consider genetic service options.

Aim 2: In a two-arm randomized intervention trial (RCT, N~2,918), to compare a message-based outreach intervention to standard outreach for effects on: survivor reach, relative reach, and uptake of appropriate cancer genetic services (i.e., genetic counseling and testing for survivors, online genetic risk assessment for relatives) among survivors of ovarian cancer identified via a state cancer registry.

Aim 3: To conduct a process evaluation consistent with the RE-AIM framework alongside the RCT to measure: reactions, dose delivered/received, fidelity, acceptability, barriers/facilitators, and alignment with ethical principles.

2.2 We hypothesize that the message-based approach will result in greater reach and uptake of genetic services than standard outreach.

3.0 **Background***

The majority of women at greatest risk for ovarian cancer due to hereditary factors are unlikely to know about their elevated risk and prevention opportunities. This significant gap in outreach means that most at-risk women will receive a late diagnosis of ovarian cancer with a dramatic negative effect on survival.¹ Traceback approaches that leverage state-wide cancer registries' ongoing surveillance activities offer a potentially low cost platform for outreach to ovarian cancer survivors and their close relatives.

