4.0 Study Endpoints*

4.1 Primary RCT outcomes: 1) Survivor reach: the proportion of the eligible survivors identified and contacted by GCR who log in to the website, 2) Close relative reach: the proportion of close relatives enumerated by survivors who log in to the website, and 3) Uptake of cancer genetic services: the proportion of untested survivors who complete telegenetic counseling and the proportion of relatives enumerated who complete B-RSTTM screening and subsequently access genetic counseling. We will evaluate secondary outcomes: In the MBI arm, we will track survivor' and relatives' patterns of website usage including: duration of time on the website, number of return visits, pages viewed, and the proportion of survivors who select different relative contact options.

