B.5.1.c. Genetic service options: We will offer free pre-test telegenetic counseling to all survivors who log in to the website, regardless of whether they complete the tasks. Two recent trials showed that similar approaches are non-inferior to face-to-face counseling.^{57,58} Survivors can opt for phone and/or video counseling via Emory HIPPA approved Zoom links. They can schedule a session (~60 min) on the study website by providing their contact information and preferred appointment date/time. We will ask survivors to review an online genetic counseling consent form and complete a brief intake survey (e.g., prior genetic testing result). Survivors may invite a support person or other family members to participate in the session. Scheduling a telegenetic counseling session indicate that participants agree to receive services provided by means of telemedicine by a genetic counselor intern at Emory University. Genetic counseling interns (supervised by Drs. [name] and [name]) will proactively contact consented survivors for the counseling sessions. Interns will be blinded to participant's/relatives study-arm assignment. All interns will have comprehensive training in cancer genetics and use of telemedicine. The intern will be trained in best practices: review personal and family medical history, discuss appropriate genetic tests (e.g., minimum *BRCA* and Lynch syndrome, other genes based on survivors' family history), and discuss the risks/benefits/limitations of recommended tests. Interns also will receive training in how to refer survivors to informational and support resources, including any local patient navigator programs to assist the participant with additional medical care needs. Participants will receive a copy of their pedigree, a medical referral letter summarizing key aspects of the counseling session and recommendations for genetic testing. We will recommend that participants share these letters with their primary care provider (PCP) as follow-up. If participant's prefer, the intern can work with the PCP to arrange genetic testing. We will also offer post-test telegenetic counseling at no cost to all participants. Medicare's covers *BRCA1/2* genetic testing for people with personal history of ovarian cancer. In addition, the Genetic Testing Fund established by Georgia CORE ([name], President and Co-I) provides access to genetic testing for hereditary breast and ovarian cancer for uninsured Georgians.⁵⁹ Since 2014, the Fund has supported testing for over 70 underinsured Georgians who would not have otherwise been able to afford it.

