
B.5.2. Close relative procedures: Relatives eligible to participate must be: 25 years or older (age recommended to initiate preventive behaviors)⁶⁰, able to access the internet, a 1st or 2nd degree relative of the survivor, able to read English, and non-incarcerated or institutionalized. Relatives will receive a unique website login linked to the survivor that enables access to the website content and describes pros/cons of family-history-based genetic risk screening for HBOC. Additionally, relatives for whom we have cell phone numbers will receive 3 cueing SMS reminders over 9 weeks (developed during Aim 1). The SMS will thank them for visiting the website and

suggest they return as needed and complete the genetic risk assessment for ovarian cancer family history. We will use the B-RST™ (developed and validated by [name] in 2009),^{61,62} which is endorsed by the USPSTF as one of several validated screening tools that is clinically useful for estimating the probability of *BRCA1/2* mutation and identifying women for referral to genetic counseling. This screener assesses personal and family history (1st and 2nd relatives) of breast cancer, bilateral breast cancer, ovarian cancer and male breast cancer, and Ashkenazi Jewish heritage. The intervention website will include a separate portal dedicated to the B-RST™ 3.1 screen. Although all 1st or 2nd degree relatives of ovarian cancer survivors will screen positive on B-RST™, completing the screener will raise participant awareness of the factors that contribute to hereditary risk of ovarian cancer and will reinforce the salience of seeking genetic counseling. We will recommend genetic counseling for all close relatives because of their heightened risk for carrying a *BRCA1/2* mutation. We will direct interested relatives to the same telegenetic counseling services provided to survivors. Ideally, we would recommend testing the survivors first, and only offer genetic testing to close relatives with a confirmed pathogenic variant ala cascade testing. However, we will offer genetic testing to relatives regardless of survivor's testing status.

B.6. Standard Outreach Arm

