Primary RCT outcomes: 1) Survivor reach: the proportion of the eligible survivors identified and contacted by GCR who log in to the website, 2) Close relative reach: the proportion of close relatives enumerated by survivors who log in to the website, and 3) Uptake of cancer genetic services: the proportion of untested survivors who complete telegenetic counseling and the proportion of relatives enumerated who complete B-RST™ screening and subsequently access genetic counseling. We will evaluate secondary outcomes: In the MBI arm, we will track survivor’ and relatives’ patterns of website usage including: duration of time on the website, number of return visits, pages viewed, and the proportion of survivors who select different relative contact options. We can also link survivor and relative patterns of use to evaluate “family” patterns of use. We will assess the proportion of survivors and relatives who self-report in the post-intervention online survey (described below) having completed genetic testing, but we will not have sufficient power to consider uptake of genetic testing as a primary outcome.

Primary data sources include: 1) GCR will record all survivor contacts (i.e., mailings, calls, messages left, call-backs), 2) website use reported by Peachtree Solutions on a monthly basis (i.e., website login and user-patterns data), and 3) genetic counseling interns’ electronic case

logbook of appointment scheduling and completion. We will limit website data collection to information regarding survivor's prior genetic counseling/testing, enumeration of relatives, and contact information for relatives with survivors' approval to contact. We will limit data collected from relatives on the website to telephone number, home address, email addresses, and to prior experiences with genetic counseling/testing. We decided against a formal survey prior to or during the intervention to minimize participant burden and to enable a cleaner evaluation of the feasibility of using the proposed intervention to maximize survivor/relative reach.

Post-intervention online survey: We will recruit survivors and relatives who logged on to the website, regardless of their level of participation. We will post a study invitation letter and a one-time 20-minute survey on the study website and send the letter to survivors and relatives with contact information (e.g., mailing address, email, or mobile phone number) about 4 weeks after the intervention phase.

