Data analysis for primary RCT outcomes: We will conduct all analyses in SAS 9.4. Because our sample is identical with the study population, there will be no missing data for the main outcome. We will code people who do not engage in primary study outcomes (e.g., visiting website) as '0', and all others as '1'. Among participants interacting with the website, we will calculate dose of web use as the number of sessions and time spent on the website as indicators of central processing. For the main trial outcomes, we will first examine distributions (frequencies and means/standard deviations) for all relevant variables. To analyze *survivor outcomes*, we will use logistic regression to analyze arm assignment as a predictor of: 1) reach and 2) uptake of genetic counseling yielding an odds ratio and 95% confidence interval for the intervention effect. For *close relatives outcomes*: 1) reach, 2) uptake of B-RST™, and 3) uptake of genetic counseling, we will conduct a logistic multilevel analysis accounting for clustering of close relatives in cancer survivors (i.e. close relatives are level-1 who are nested in level-2). Given the binary nature of the outcomes, we will assess dispersion and adjust for over- or under-dispersion in our analyses. Subsequently, we will conduct moderator analyses to see for whom the intervention worked best. These analyses will entail expanding the described logistic regression/logistic mixed models to include direct effects of a proposed moderator (e.g. age at diagnosis) and an interaction effect between the moderator and arm assignment. Although the main outcomes will have no missing data, our covariates might have missing data. We will assess patterns of missingness and use appropriate methods (i.e. full-information maximum likelihood estimation or multiple imputations) to account for missing data.

Data analysis for post-intervention online survey: To evaluate factors suggested by information processing theories that are associated with the intervention, we will conduct quantitative

PROTOCOL TITLE: Testing a Low Cost Population- and Theory-Based Outreach Intervention to Engage Ovarian Cancer Survivors and their Close Relatives to Consider Genetic Services.

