Aim 2 (message-based intervention and waitlist standard outreach approaches): The GCR will identify eligible cancer survivors and provide them with website access information. Upon entry to the study website, we will provide survivors with an explanation of the study and the opportunity to continue or to decline. The online consent form ends with the "I agree" checkbox so the participant can decide whether they still want to participate after reading the listed conditions. Those who agree to participate and include their mobile phone number will receive cueing SMS reminders from the study team. Survivors who select choice options that involve the study team doing outreach on the survivor's behalf will receive an additional prompt to provide consent and contact information (e.g., mailing address, email, phone number) of first and second degree relatives. Relatives, contacted by the survivor or permitted to be contacted by the study team will receive a unique website login that is linked to the survivor and enables access to a consent form on the study website that describes the study procedures, potential benefit and risks, privacy and confidentiality of protected health information. Same as survivors, relatives who click the "I agree" button on the informed consent webpage would indicate consent. Relatives in the MBI arm who log in to the website and are willing to provide a mobile phone number also will receive cueing SMS reminders from the study team. All relatives who consent to participate will be directed to complete B-RST™ and the same tele-genetic counseling services.

All survivors and relatives who log in to the website, regardless of whether they complete the tasks, will have access to the same pre-test telegenetic counseling. Survivors can opt for phone and/or video counseling via Emory HIPPA approved Zoom links. Participants will be asked to review online a genetic counseling consent form. The consent form will include information about the procedures of genetic counseling, potential benefits and risks, privacy and confidentiality of protected health information, and contact information for the Emory IRB and study team. Verbal consent will be obtained by the genetic counselor intern from the participant prior to the counseling session.

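### The relatives' uptake outcome has conflicting definitions (B-RST then counseling, each separately, or B-RST alone); under the Section 4.1 rule, counseling without a prior B-RST counts as failure and could inflate the MBI effect

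*Combined protocol and SAP*

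**What the plan says.** Four places define what counts as uptake for relatives, and they differ.

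- **Sections 4.1 and 6.4** (primary outcomes): "the proportion of relatives enumerated who complete B-RSTTM screening and subsequently access genetic counseling". Both events are required, in that order, among relatives enumerated.
- **Section 17.0, data analysis**: the relative outcomes are "1) reach, 2) uptake of B-RST™, and 3) uptake of genetic counseling". Counseling stands alone, with no B-RST condition.
- **Section 17.0, Table 3**: the relative primary outcomes are reach (985 versus 219) and B-RST uptake (394 versus 44). The second pair is relatives who log in, not relatives enumerated. Relative counseling has no row.
- **Section 2.1, Aim 2**: the appropriate services are "genetic counseling and testing for survivors, online genetic risk assessment for relatives".

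On the role of the screener, Section 6.1 B.5.2 says: "Although all 1st or 2nd degree relatives of ovarian cancer survivors will screen positive on B-RST™, completing the screener" is meant to raise awareness and make counseling more salient. The same section recommends counseling to all close relatives.

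On access, Section 22.0 says: "All survivors and relatives who log in to the website, regardless of whether they complete the tasks, will have access to the same" pre-test counseling. Section 6.1 B.6.2 gives standard-arm relatives the same service. Section 24.0, on the genetic counseling training program, describes services for relatives who complete the B-RST, which can be read as a restriction. Section 6.1 B.5.1.c adds a further route: "Survivors may invite a support person or other family members to participate in the session".

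**The concern.** A primary outcome with several unreconciled definitions leaves it open which one will be reported as the result. The definitions can also give different answers.

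The screener selects nobody here, because every eligible relative is positive and every one is advised to have counseling. Requiring a completed B-RST first therefore adds nothing to a measure of counseling received. It can, however, discard counseling that took place. The intervention also promotes the required step directly: MBI relatives with a cell number on file get three text messages that encourage the risk assessment, and none are described for the standard arm. If some relatives are counseled without B-RST, the two-step rule would hide a larger share of counseling in the control arm than in the MBI arm.

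**Working it through.** **1. The plan's own figure.** Table 3's sample sizes follow from its assumptions (75% of logged-in survivors enumerate a median of 2 relatives, Section 13.0):

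- Enumerated: 1,459 × 0.45 × 0.75 × 2 = 984.8 (MBI); 1,459 × 0.10 × 0.75 × 2 = 218.9 (control).
- Logged in: 985 × 0.40 = 394; 219 × 0.20 = 43.8.

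Power for B-RST uptake is Φ[(|p1 − p2| − 1.96·SE0)/SE1], with SE0 from the pooled proportion, SE1 unpooled, and each n divided by the design effect. Alpha is not stated; 0.05 two-sided is assumed. With design effect 1.3, the sample sizes are 394/1.3 = 303.1 and 44/1.3 = 33.8. Then SE0 = 0.0859 and SE1 = 0.0831, so power = Φ[(0.40 − 0.168)/0.0831] = 0.997. With design effect 2 it is 0.968. The stated >.99 reproduces, but for B-RST alone among relatives who log in.

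**2. What the 4.1 rule measures compared with any counseling.** Let q be the counseling rate among B-RST completers, and r·q the rate among logged-in relatives who skip B-RST. Take q and r as equal in the two arms. Neither is in the documents. With reach 40% and 20%, and B-RST 70% and 30%, per enumerated relative:

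- 4.1 outcome: 0.40 × 0.70 × q = 0.28q (MBI); 0.20 × 0.30 × q = 0.06q (control). Risk ratio 0.28/0.06 = 4.67 for any q or r.
- Any counseling: 0.40 × (0.70 + 0.30r) × q (MBI); 0.20 × (0.30 + 0.70r) × q (control).

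| r (assumed) | Any counseling, MBI / control | Its risk ratio | 4.1 ratio ÷ this ratio | Counseled relatives scored as failures, MBI / control |
|---|---|---|---|---|
| 0 | 0.280q / 0.060q | 4.67 | 1.00 | 0% / 0% |
| 0.25 | 0.310q / 0.095q | 3.26 | 1.43 | 10% / 37% |
| 0.5 | 0.340q / 0.130q | 2.62 | 1.78 | 18% / 54% |
| 1 | 0.400q / 0.200q | 2.00 | 2.33 | 30% / 70% |

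The last column is 1 − (4.1 outcome ÷ any counseling). At r = 0.25 in the control arm, for example, it is 1 − 0.060/0.095 = 37%.

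**3. Power for relative counseling.** Table 3 gives none. By the same formula, with 985 and 219 enumerated and design effect 1.3, q = 0.1, 0.3 and 0.5 give 0.34, 0.94 and 0.999 for the 4.1 outcome. For any counseling at r = 1 they give 0.19, 0.64 and 0.90. Power for counseling therefore depends on a rate that the plan has not stated.

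**The case against.** The best defense is that Section 17.0 already analyzes counseling without a B-RST condition, so nothing is misscored if that section governs. This stands in part: the misscoring is conditional. But Section 4.1 is where the primary outcomes are declared, Section 6.4 repeats it, and nothing says which text prevails.

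A second defense is that nobody may reach counseling without B-RST. The documents use the word task for the survivor's small and large asks and never for B-RST. The sentence before the access statement in Section 22.0 directs consenting relatives to B-RST, and Section 24.0 points the same way. This also stands in part: open access is the natural reading of Section 22.0, but it is not settled, and the number counseled without B-RST may be zero. Section 6.1 B.5.2 expects the screener to encourage counseling, so r = 1 is an extreme case.

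A reader might go further and infer that the 4.1 rule would manufacture an MBI effect on counseling where none exists. The documents do not support that. It would hold only among relatives who log in, and 4.1 counts relatives enumerated. On that denominator, equal counseling among those who log in still gives MBI a real ratio of 2.00, from reach of 40% versus 20% alone. The rule can exaggerate this effect; it does not create it.

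A reader might also want to credit relatives who sit in on the survivor's session. Nothing says that such attendance is the relative's own counseling. Counting it would carry survivor uptake, itself planned at 70% versus 30%, into a relative outcome.

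**Conclusion.** The relative-uptake primary outcome is inconsistently defined in both event and denominator; that follows from the text alone. The bias is conditional. It arises only if the 4.1/6.4 rule governs and some relatives are counseled without or before B-RST. Its direction, in favor of MBI, rests on the planned 70% versus 30% B-RST completion. Its size rests on r, which is assumed: the 4.1 risk ratio of 4.67 overstates the ratio for any counseling by a factor between 1.00 (r = 0) and 2.33 (r = 1). The table also assumes the plan's reach rates, and equal q and r in the two arms. It does not model relatives counseled first and screened later, who would also be misscored.

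**What to change.** - In Sections 4.1 and 6.4, replace the two-step outcome with the two already in Section 17.0: (a) B-RST completed; (b) the relative's own genetic counseling session accessed, counted whether or not B-RST was done and in whichever order. Use relatives enumerated as the denominator for both.
- Report the sequence from B-RST to counseling by arm, as description only. Record attendance at a survivor's session in the same way, not as relative uptake.
- Put Table 3's B-RST row on the enumerated denominator. The planned rates become 0.40 × 0.70 = 28% of 985 and 0.20 × 0.30 = 6% of 219, and power stays above .99 at design effects 1.3 and 2. State that Table 3 gives no power for relative counseling, or add a row with an explicit counseling rate.
- Reconcile Sections 22.0 and 24.0 on whether a relative can have counseling without completing B-RST.

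The cost is wording, one revised table row, and a logbook field if session attendance is to be recorded. Website records and the counseling logbook already supply outcomes (a) and (b). No participants or procedures are added.

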5.0 Study Intervention / Design

We propose a multi-component, low cost, message-based communication outreach intervention to engage ovarian cancer survivors and their at-risk relatives in considering cancer genetic services. The intervention includes foot-in-the-door techniques, tailored/targeted print, website support, and short messages to expand reach of prevention messages. An outreach website with content for both survivors and close relatives will be the hub channel in the communication intervention wheel. In turn, we will encourage access to the website using other communication channels as

spokes in the wheel including: 1) Initial print-based contact to survivors sent by the cancer registry, 2) additional briefer reminder postcards and short text message cues (SMS), 3) additional short text message cues sent directly to close relatives (with contact information and permission provided by the survivor).

6.0 Procedures Involved*

6.1 *Describe study procedures.*

Study Overview: We propose two phases of study activities. **Phase 1** (Aim 1) comprises 12 months of collaboration with survivor/family working groups to develop: targeted letters, choice options for relative outreach, and content for an interactive website, and short cueing messages that engage ovarian cancer survivors and their at-risk relatives in considering genetic risk assessment. **All of these study materials will be submitted as an IRB amendment prior to fielding.** **Phase 2** (Aims 2-3 – Years 2-4), is an RCT that compares the message-based intervention (MBI) with current standard outreach. We will evaluate the following outcomes: survivor reach, at-risk relative reach, and uptake of appropriate cancer genetic services and conduct a process evaluation based on the RE-AIM framework that includes survivors and relatives (Aim 3).

A. Aim 1: Develop a scalable message-based outreach intervention.

A.1. Overarching Approach: We base our community partnerships on the combined principles and methods of community-based participatory research and citizen science.²¹ We propose to bring the issue of increasing reach to the community of ovarian cancer survivors and families and engage their collaboration to develop appealing messages to expand the reach of genetic services to survivors and close relatives. Community members with relevant experience will work with us as citizen scientists using their experiences and skills to help develop messages.²¹ We will hone ovarian cancer survivor/family partners' skills as citizen scientists by familiarizing them with theories of information processing, relational autonomy and distributive justice (see below). The overarching objective is to co-create content that has the greatest potential to engage survivors/relatives to thoughtfully consider the tradeoffs of genetic service uptake. [name], [name] and Peachtree Solutions have considerable experience working with community advisory boards (CABs) and end users. [name] has conducted qualitative research to develop genetic risk messages in a variety of settings in the U.S. and abroad.²²⁻²⁴

A.2. Study Population and Procedures: Development of the MBI will involve three iterations and the following stakeholders: 1) community members who have a personal and/or family history of ovarian cancer; 2) communication and bioethics experts (Drs. [name], [name], [name], [name], Emory's Visual Medical Education team); and 3) cancer genetics content experts (Drs. [name], [name], [name]). Georgia CORE's CABs will help us identify 35-40 community members via snowball sampling to participate in working groups (see letters of support). We will share eligibility criteria with Georgia CORE (e.g. ovarian cancer survivor/family, access to the internet and being available for in-person or online group discussions). [name] (Co-I) will oversee these activities with the assistance of an ethics fellow and a research assistant. In assembling the working groups, study staff will conduct additional eligibility screening (e.g., prior experience with cancer genetic services, family size) to increase the diversity of community members for

working group activities. We will subdivide the community members based on their expertise and preference into 3 working groups consistent with a citizen science philosophy. Each group will contain 5-10 survivors and/or close relatives who will work on specific tasks and intervention-related products. Participants will receive \$500 for attending 2-3 90-minute in-person meetings and some additional outside “homework”. For each in-person working group session, we will prepare an interactive didactic module with lay explanations of theory-based concepts related to the working group’s task. The remainder of the session will focus on a specific task (e.g., plans to interview other family members to solicit example experiences, preference for being contacted). We will give working groups ongoing updates as the study progresses and share the study results in a final discussion group half-day meeting described in Aim 3.

A.3. Working Group Procedures: [name] who has experience working with community groups and evaluating websites that link those with inherited disease to genetic services will oversee working group activities.²⁵ In *iteration 1*, one community working group will recommend approaches for framing the “large ask” and choice sets for relative contact options. A second and third working group will assist in collecting survivor-family stories using photonovela or other strategies. In *iteration 2*, content experts in communication, genetics and ethics will assemble working group content and develop initial formats for the website and print materials. Communication and bioethics experts will review materials for alignment with communication frameworks and ethical principles. Next, Peachtree Solutions (see letter of support), our web-development partner, will work with Emory’s Visual Medical Education team to draft the website and print materials. In *iteration 3*, a third community working group will review initial and revised iterations of intervention content using systematic cognitive interviewing methods.²⁶ Peachtree Solutions has extensive experience with the latest usability standards and will direct the usability testing. The investigative team and consultants will make revisions based on each round of panel input. We will use the Suitability Assessment of Materials (SAM) and Comprehensibility (CAM) scale to evaluate the readability and comprehensibility of the website with the aim to develop a website that users’ rate as “superior”, indicating it is easy to use and understand, low in cognitive demand, attention-getting, and motivating.²⁷

Prior to fielding the trial, we will submit the developed study materials as part of IRB amendment.

[figure not shown]
B. Aim 2: Conduct a two-arm randomized intervention trial (N~2,918).

B.1. Study Design: We will compare the message-based intervention (MBI) developed in Aim 1 to standard outreach in a two-arm RCT in Years 2 and 3. The MBI comprises a combination of novel intervention components that depart sufficiently from prior research to warrant a comparison arm (with access to the MBI website when the trial period is completed).²⁸ Figure 2 displays the flow of the intervention.

B.2. Study Population: Study activities will take place in Georgia (GA), where about 615 women are diagnosed with ovarian cancer and about 395 die from the disease each year.²⁹ We propose a population-wide recruitment approach and will use Georgia Cancer Registry (GCR) to retrospectively identify, screen, and enroll all living ovarian cancer patients in GA, diagnosed between January 2005 and December 2017. GCR contains information on demographic characteristics, condition at time of diagnosis (e.g., stage, histologic types, and other clinical and

Figure 2: Intervention design flow chart

demographic variables), and treatment history of all cancer patients in GA.²⁹ Since 2001, the database excludes borderline (low malignant potential) neoplasms. We will consider women in GCR for study participation if they meet four criteria: 1) diagnosed with ovarian, fallopian tube, or peritoneal cancers; 2) lived in GA at the time of diagnosis; 3) are not deceased per the registry's records; and 4) have a mailing address. Our review of registry files as of May 2019 revealed: of the 8,760 women with a diagnosis of ovarian, fallopian tube, or peritoneal cancer, excluding those who were deceased or lost to follow as of 2017, we will have addresses for approximately 2,918 survivors during the 16-month recruitment period. GA is the 8th largest state with almost 10.5 million residents; 1.8 million (~17%)³⁰ residents live in rural areas.³¹ The state enjoys substantial racial-ethnic diversity: 32% of the state is Black or African American alone (4th largest African American population in the U.S.), 9.6% is Hispanic or Latino and 4.2% is Asian alone, 15% of the population lives in poverty, and 15% lack health insurance.³⁰

The efficient recruitment of survivors presents logistical challenges particularly given the high mortality rate of ovarian cancer. We made the deliberate decision to reach out to ovarian cancer survivors diagnosed back to 2005 based on: 1) our message-based communication traceback approach that targets ovarian cancer survivors with short- and long-term survivorship to include diagnoses that predated changes in testing guidelines³²; 2) survivors diagnosed more than a decade ago are underrepresented in the majority of case identification trials with self-selected samples in specialty clinical settings; 3) we expect rates of recruitment and enrollment to decline as we trace back; however, we will potentially maximize the total reach and learn about the intervention efficacy across a range of survivor periods; and 4) the cost advantage of using the state-wide cancer registry to identify all of the locatable survivors in GA counterbalances

recruitment drawbacks. [name] has used similar location and outreach strategies in collaboration with GCR to promote mammography and achieved 63% participation rates.³³ Others also have used cancer registries to recruit breast and ovarian cancer survivors into clinical trials for preventive cancer activities; they contacted survivors zero to nine years post-diagnosis, with most reporting response rates between 30-40%.³⁴⁻⁴²

B.3. Randomization: We will randomly assign cancer survivors (N=2,918) in a 1:1 ratio to either the MBI arm (n=1,459) or the waitlist standard outreach arm (n=1,459). Given our access to the entire population of ovarian cancer survivors in GA and characteristics of their cancer and treatment, we will use a covariate adaptive randomization procedure.^{43,44} In this procedure, we will randomly assign the first participants to a group, then will assign subsequent participants to a particular group by taking the covariates and previous assignment into account to adapt the probability of group assignment. This approach ensures our randomization is superior to simple randomization that only works perfectly for very large samples.⁴⁵ It will result in a covariance balanced allocation and thus avoid potential influence of covariates on the intervention results. We will use the SAS macro developed by Colavincenzo to execute the randomization.⁴⁶ We will choose covariates we expect are related to reach from the cancer registry data. Examples are year of diagnosis and age at diagnosis. Registry staff will randomize identified survivors to arm using sequentially numbered and sealed envelopes.

B.4. GCR Recruitment Procedures: The proposed recruitment procedures comply with GCR's current standards. We adapted them from strategies that were effective in other studies using cancer registry for recruitment^{34,39,42,47,48} that will allow for sustaining and disseminating the intervention beyond the study. We will classify survivors who log in to the study website as "reached." Recruitment will rely on multiple communications aimed to encourage survivors to log in to the study website with the number of contacts largely identical for both arms (Figure 4).

B.4.1. First contact letter (MBI arm only): We will mail survivors in the MBI arm a one-page infographic (See "U01 MBI infographic draft") that includes a postage-paid return envelope to return their responses to three questions (See "U01 MBI three questions draft"). Responses will help us better understand information needs of families affected by ovarian cancer. Participants may answer the questions online by using a QR code, or write their responses on the enclosed document and return it to GCR. Responses will be anonymous and will not be linked to any personal identifiable information. We will not report participants' responses for research purposes and their responses will be reported on an aggregate level (e.g., number of envelopes returned).

[figure not shown]
B.4.2. First mail-out: This mailing will be sent approximately 7-10 days after mailing the first contact letter, we will mail to survivors in both arms \$5 cash as a token of appreciation for their attention, and a recruitment packet based on their arm assignment: targeted print material in the MBI arm versus standard study invitation letter in the standard outreach arm. GCR staff will mail recruitment materials in batches of about 172 every month. We will use Accurint, a LexisNexis database with coverage across the US, to obtain the most current address for registry survivors in an effort to maximize reach of the mailed material on the initial attempt. The materials will instruct participants to contact the toll-free registry telephone number with questions or concerns. Throughout recruitment, we will perform monthly checks to avoid

initiating contact with a recently deceased woman. To reduce unnecessary contact attempts by GCR, the intervention coordinator will provide GCR with the IDs of survivors who have logged in to the study website on a biweekly basis.

B.4.3. Telephone contacts: Studies show that interpersonal communications, such as a personal phone call, can increase clinical trial accrual when combined with informational handouts.⁴⁸⁻⁵³ Two weeks after mailing each packet, GCR will contact survivors by phone who do not log in to the study website. We will call survivors every 2-3 days for up to 9 attempts, after which we will categorize them as inaccessible. The phone call aims to: 1) check on receipt of the recruitment packet; 2) remind survivors to log in to the study website; and 3) answer questions regarding the study. This schedule is the standard for GCR outreach.

B.4.4. Second mail-outs: Survivors who do not log in to the study website within 2 weeks of the last phone call attempt will receive a second mail-out containing the full recruitment packet.

B.5. Message Based Intervention (MBI) Arm: In collaboration with the working groups we will develop messages to increase perceived relevance (e.g., photonovela stories), and prompt website access (e.g., SMS reminders of passwords). Messages will be included in: a website hub, initial print-based contact to survivors sent by the cancer registry, reminder postcards and short text message cues (SMS) for survivors and close relatives (when contact information and permission is provided by the survivor). We will work with Emory's Visual Medical Education team

of certified medical illustrators to design illustrations for these products to increase the accessibility of complex medical concepts.

B.5.1. Survivor components: We will send the initial full recruitment packet to identified survivors randomized to the MBI arm. The packet will contain theory-based targeted messages developed in Aim 1, and a cover letter that explains how we identified the woman, and provide her with a unique login to access the website that we can track and link the survivor to the cancer registry. Figure 3 displays the intervention flow.

